5.2. Demographic and Baseline Characteristics

All demographic and baseline characteristic data will be summarized by treatment group using descriptive statistics for all subjects in the ITT-E population.

The summary table will include age, age category (<65, \geq 65 years), ethnicity, race, baseline UUI episodes per day (\leq 3, $>$ 3) (as randomized and actual baseline), presence or absence of DO (site and central assessments), previous use of onabotulinumtoxinA (naïve vs. prior use) (as randomized and actual baseline), weight, height and body mass index (BMI).

The actual baseline for UUI episodes per day is derived based on the logic described in [Section 4.3.2.1](#). The actual previous use of onabotulinumtoxinA status is based on searching for the preferred term of “BOTULINUM TOXIN TYPE A” in subject’s medications taken before randomization.

Age (years), height (cm), weight (kg), and BMI (kg/m^2) captured at Screening will be summarized as a continuous variable.

All demographic data will be listed.

5.3. Medical History and Concomitant Disease

Descriptions of medical history findings will be coded using Medical Dictionary for Regulatory Activities (MedDRA) version 22.1 or higher.

A disease or illness reported as medical history without a start date will be included in medical history without a date assigned. Medical history will be sorted by descending overall frequency, by system organ class (SOC) and preferred term (PT) in the summary table. Medical history data listings will be sorted by treatment, subject number, start date, SOC and PT.

5.4. Prior and Concomitant Medication

Prior and concomitant medications will be coded using the World Health Organization (WHO) Drug B3-Sept Format, 2019 version. These medications will be further classified as follows.

- Prior medication is defined as those medications that started prior to the study treatment.
- Concomitant medication is defined as those taken on or after the study treatment. If medications started prior to the study treatment and were ongoing after the study treatment, those medication will be considered as concomitant medication as well.

The number and percentage of subjects taking prior and concomitant medications will be summarized overall by Anatomical Therapeutical Chemical (ATC) Levels 2 and 4 for all subjects in the safety population. Prior and concomitant medications will be listed for all subjects in the safety population.

5.4.1. Additional OAB Treatment

Starting at Week 24 and after (at clinic visit, phone visits or between visits), subjects can request and be prescribed additional OAB treatment(s). A treatment is considered additional OAB treatment if on the “Concomitant Medications/Procedures” eCRF the answer to “Is this an additional OAB medication” is “Yes”, regardless of when the additional OAB treatment was received.

The additional OAB medication will be summarized by ATC level 2, 4, and Preferred Term while additional OAB procedures will be summarized by preferred term. Separate listings for additional OAB medications and procedures will be provided.

6. EFFICACY ANALYSIS

In general, the ITT-E will be used for all analyses of efficacy endpoints unless stated otherwise.

6.1. Continuous Efficacy Endpoints

For continuous efficacy endpoints, the by-visit means and SD, as well as change from baseline estimated with least squares means, standard error, and 95% confidence intervals (CI) will be presented for each treatment group and the difference between each dose group relative to placebo. Nominal p-values from comparisons from each dose group relative to placebo will be provided for descriptive purposes. The change from baseline will be analyzed by a mixed model for repeated measures (MMRM) with restricted maximum likelihood estimation incorporating all applicable post-baseline visits. For average daily number of urge urinary incontinence (UII) episodes, the MMRM model will include terms for treatment, visit, visit by treatment interaction term, baseline value, and previous use of onabotulinumtoxinA as randomized (naïve vs. prior use). For the other endpoints, one additional term of baseline UII episodes per day category as randomized (≤ 3 vs. > 3) will be included in the MMRM model. If any of the stratification factors has a stratum with number of subjects less than 5, the factor in question will not be included in the MMRM model. If $>15\%$ of the subjects were incorrectly stratified based on the actual baseline UII episodes per day and previous use of onabotulinumtoxinA, a sensitivity analysis using the same MMRM model but with actual values of the two stratification factors as covariates will be carried out.

The Kenward-Roger adjustment will be used with restricted (or residual) maximum likelihood (REML) to make statistical inference. An unstructured covariance matrix will be used to model the correlation among repeated measurements. If the unstructured covariance model fails to converge with the default Newton-Raphson algorithm, the Fisher scoring algorithm will be used to provide initial values of the covariance parameters. In the rare event that none of the above methods yield convergence, the following structures will be investigated: heterogeneous Toeplitz, Toeplitz, heterogeneous First-Order Autoregressive [AR (1)],

heterogeneous compound symmetry (HCS), and compound symmetry (CS). The covariance structure converging to the best fit, as determined by Akaike's information criterion (AIC), will be used.

[figure not shown]
Results will be presented in terms of least square means (LSMEANS), treatment differences in LSMEANS, nominal p-value and 95% confidence intervals for the treatment difference for all timepoints. Type III p-values for all factors in the MMRM model will be listed on the table.

An example of the SAS code for the base procedure is given below:

```
proc mixed data = datain method = reml;
  class subject treatment visit UUI_cat onabA_use;
  model CFB = treatment visit treatment*visit baseline UUI_cat onabA_use;
    /ddf=KR solution chisq;
  repeated visit / subject=subject type=UN r rcorr;
  lsmeans treatment*visit / pdiff=all cl alpha=0.05;
run;
```

The normality assumptions for the primary analysis model will be assessed by inspection of the residuals from the model and normal probability plots. If assumptions of normality are grossly violated, additional supportive analysis of the data will be performed in order to assess the robustness of the conclusions drawn from the primary analysis.

Sensitivity analyses using analysis of covariance (ANCOVA) will be carried out for change from baseline at Week 12 in average daily number of UUI episodes and micturitions. The model will use the change from baseline data at Week 12 and include treatment arms and baseline value as covariates.

The following efficacy endpoints will be summarized and analyzed in this fashion (Data for all visits will also be presented):

- Change from baseline at Week 12 in average daily number of UUI episodes
- Change from baseline at Week 12 in average daily number of micturitions
- Change from baseline at Week 12 in average daily number of UI episodes
- Change from baseline at Week 12 in average daily number of urgency episodes
- Change from baseline at Week 12 in average volume voided per micturition

- Change from baseline at Week 12 in total summary score from I-QOL
- Change from baseline at Week 12 in OAB-q scores
- Change from baseline at Week 12 in average daily number of nighttime voids

For all domains and subscales in I-QOL and OAB-q the mean value and change from baseline will be summarized by visit.

6.2. Categorical Endpoints

The following categorical endpoints are included in this study (Data for all visits will also be presented)

- Proportion of subjects who has $\geq 50\%$ reduction from baseline in UUI episodes at Week 12
- Proportion of subjects who has $\geq 75\%$ reduction from baseline in UUI episodes at Week 12
- Proportion of subjects who has 100% reduction from baseline in UUI episodes at Week 12
- Proportion of subjects who has $\geq 50\%$ reduction from baseline in average daily number of UI episodes at Week 12
- Proportion of subjects who has $\geq 75\%$ reduction from baseline in average daily number of UI episodes at Week 12
- Proportion of subjects who has 100% reduction from baseline in average daily number of UI episodes at Week 12
- Proportion of responders (subjects who achieve MID for I-QOL total score) at Week 6 and 12
- Proportion of responders based on the PGI-C scale score at Week 12

The Cochran-Mantel-Haenszel (CMH) common risk difference estimate stratified by the updated stratification factors (baseline UUI episodes per day (≤ 3 vs. > 3), and prior onabotulinumtoxinA use (naïve vs. prior use)) used during randomization with weights proposed by Greenland and Robins [3] will be used to compare the proportion of responders between the active and placebo groups. If there is a stratum for a treatment group that has 0 subjects in it, the 0 count will be replaced by 0.5 in order to prevent dividing by 0 as suggested in Greenland and Robins. The estimated common risk difference, and associated p-value and 2-sided 95% confidence interval will be tabulated.

Other PGI questions collected on the PGI form, i.e. PGI-severity, PGI-control, PGI-frequency, and PGI-leakage will be summarized with count and frequency of each response at Week 12.

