For Cohorts 1a, 1b, and 2, stratification factor for baseline UUI episodes is based on the average number of UUI episodes per day recorded over the 3-day diary period at baseline (ie,  $\leq 3$  vs.  $> 3$  UUI episodes per day).

For Cohort 1a, the urodynamic assessment where an evaluation of the presence or absence of DO is performed to be used as a randomization factor, must be conducted at Visit 2 prior to performing the actual randomization procedure. For subjects with a valid historical urodynamic study (per protocol [Section 8.2.3](#)), the presence or absence of DO would already be known.

For Cohorts 1b and 2, onabotulinumtoxinA treatment for urological indications must have occurred at least 12 months prior to starting the Screening Bladder Diary. Enrollment for subjects with previous onabotulinumtoxinA use will be capped at 50% of the total subject population per cohort. Subjects randomized to Cohort 1a will be assigned to the onabotulinumtoxinA naïve stratum for all analyses.

Subjects will be centrally assigned to randomized study drug using an IWRS and the randomization schedule generated by the sponsor or designee. Before screening is initiated at each site, login information and directions for the IWRS will be provided.

The IWRS will be programmed with blind-breaking instructions. In case of an emergency, the investigator or designee has the sole responsibility for determining if unblinding of a subject's study drug assignment is warranted. Subject safety must always be the first consideration in making such a determination. If the investigator decides that unblinding is warranted, the investigator should make every effort to contact the Sponsor or designee prior to unblinding a

subject's study drug assignment unless this could delay emergency treatment of the subject. If a subject's study drug assignment is unblinded, the Sponsor or designee must be notified within 24 hours after breaking the blind. The date and reason that the blind was broken must be recorded in the source documentation.

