1.2. Study Design

1.2.1. Overall Study Design

This is a multicenter, randomized, double-blind, placebo-controlled, single-treatment, 2-cohort, dose-escalation study.

URO-902 24 mg will be administered as intradetrusor injections to subjects in Cohort 1. An independent Data and Safety Monitoring Board (DSMB) will make the recommendation

regarding dose escalation only after unblinded review of safety data once all subjects in Cohort 1 reach Week 6 (or prematurely discontinue). Randomization at the higher dose (URO-902 48 mg) will begin only after the DSMB has recommended it is safe to proceed to Cohort 2

- Cohort 1: URO-902 24 mg and matching placebo
- Cohort 2: URO-902 48 mg and matching placebo

An estimated total of 78 subjects will be enrolled into 2 cohorts with approximately 39 subjects randomized into each cohort. In both cohorts, subjects will be randomized in a 2:1 ratio to receive either URO-902 (24 mg or 48 mg) or placebo. Each cohort will be randomized separately, and enrollment will be sequential, starting with Cohort 1 (URO-902 24 mg [n = 26] and placebo [n = 13]) and followed by Cohort 2 (URO-902 48 mg [n = 26] and placebo [n = 13]).

[figure not shown]
Prior to protocol amendment 1, subjects in Cohort 1 were randomized based on two stratification factors: baseline UUI episodes per day (≤ 3 vs. > 3 UUI episodes per day), and presence and absence of detrusor overactivity (DO). Post-protocol amendment 1, subjects were randomized based on a new randomization scheme and presence or absence of DO was replaced with prior onabotulinumtoxinA use. All subjects randomized prior to and post amendment 1 will have the baseline UUI episodes per day as a stratification factor. The subjects randomized under the original randomization scheme will be considered Cohort 1a and subjects randomized under the new randomization scheme will be considered Cohort 1b. For reporting purposes, Cohort 1a and Cohort 1b will be combined and subjects enrolled in Cohort 1a will be considered onabotulinumtoxinA naïve.

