1.2.3. Statistical Hypotheses

The study has no formal statistical primary endpoint hypothesis. The intent is to estimate the treatment effect of each dose group relative to placebo. For the final analysis, the subjects receiving placebo from Cohort 1 and Cohort 2 will be pooled.

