4.1.2. Testing Strategy and Multiplicity Adjustments

No formal multiplicity adjustment will be performed. Nominal p-values will be provided for all exploratory efficacy analysis as a measure of the strength of association between the endpoint and the treatment effect rather than formal tests of hypotheses.

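### The 0.5 substituted for an empty treatment-by-stratum cell in SAP 6.2 is not needed by the Mantel-Haenszel risk difference and, taken literally, gives a one-arm stratum weight and an invented 0% response rate

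*SAP*

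**What the plan says.** SAP 6.2 lists eight responder proportions. It compares active with placebo by a CMH common risk difference stratified by baseline UUI (≤3 v >3 per day) and prior onabotulinumtoxinA use, which makes four strata. The rule for empty cells is "If there is a stratum for a treatment group that has 0 subjects in it, the 0 count will be replaced by 0.5". The sentence adds that the count "will be replaced by 0.5 in order to prevent dividing by 0 as suggested in" the methods paper cited as SAP reference 3. It then says: "The estimated common risk difference, and associated p-value and 2-sided 95% confidence interval will be tabulated". No formula is printed. The text does not say which terms receive the 0.5 or what responder count goes with it.

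Several provisions bear on how thin the strata may be:

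- SAP 1.2.1: "Cohort 1a and Cohort 1b will be combined and subjects enrolled in Cohort 1a will be considered" naïve to the toxin.
- Protocol 6.5: "Enrollment for subjects with previous onabotulinumtoxinA use will be capped at 50% of the total subject population per cohort". No minimum is set.
- SAP 1.2.3: for the final analysis, "the subjects receiving placebo from Cohort 1 and Cohort 2 will be pooled".
- SAP 6.1, for the MMRM only: "If any of the stratification factors has a stratum with number of subjects less than 5, the factor in question will not be included".
- Protocol 9.5.1 makes stratification conditional on more than 5 subjects per stratum. The condition sits in the MMRM paragraph and is not repeated where the CMH method is described. SAP section 9 does not list it as changed.

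SAP 4.1.2 presents the nominal p-values as a measure of association between "the endpoint and the treatment effect rather than formal tests of hypotheses".

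**The concern.** A stratum with subjects in only one of the two compared arms holds no within-stratum comparison. A stratified risk difference should therefore draw nothing from it, and the Mantel-Haenszel weight already ensures this. Replacing the subject count by 0.5, if done as written, overrides that: the stratum gains positive weight, and the empty arm is treated as if it had been observed with no responders. The estimate moves and its standard error shrinks although no data were added.

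Missing responder data count as non-response (SAP 4.2.3), so cell sizes depend only on who was treated. One empty cell would therefore recur across all eight endpoints and every visit shown.

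**Working it through.** **Inputs.** There are 26 subjects per group, placebo being 13 + 13 pooled (SAP 1.2.1, 1.2.3, 1.2.4), and four strata (SAP 6.2). The documents give no figure for the categorical analysis, so there is none to reproduce. The responder counts and stratum sizes below are assumptions.

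**Step 1: does the estimator need a correction?** Let a of n1 active and b of n0 placebo subjects respond in a stratum, with N = n1 + n0.

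RD = Σ[(a·n0 − b·n1)/N] / Σ[n1·n0/N]

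If n1 = 0, then a = 0. The numerator term is (0·n0 − b·0)/n0 = 0 and the weight is 0·n0/n0 = 0. The stratum drops out with no division by zero. A 0/0 arises only if the program forms the stratum rate a/n1 separately, or divides by n1·n0 in a variance term.

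**Step 2: the weight under the literal rule.** With m subjects in the other arm, the weight becomes 0.5m/(m + 0.5): 0.333 for m = 1, 0.400 for m = 2 and 0.444 for m = 4, instead of 0.

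**Step 3: illustration, 26 v 26.** The SAP prints no variance formula. The usual sparse-data form is assumed:

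Σ[(a(n1−a)n0³ + b(n0−b)n1³)/(n1·n0·N²)] / (Σw)², where w = n1·n0/N.

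Active cell empty (6/13 v 4/11, 5/11 v 3/10, 1/2 v 1/3, empty v 1/2):

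- Stratum omitted: numerator 14/24 + 17/21 + 1/5 = 1.593; weights 143/24 + 110/21 + 6/5 = 12.396; RD = 12.8 points. The variance terms sum to 2.907, so SE = √2.907/12.396 = 13.8 points.
- Literal rule: the numerator gains (0·2 − 1·0.5)/2.5 = −0.200 and the weight gains 0.5·2/2.5 = 0.400. RD = 1.393/12.796 = 10.9. The variance sum rises only to 2.927, because the invented cell carries no binomial variance of its own. SE = √2.927/12.796 = 13.4.

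| Case | Stratum omitted | 0 of 0.5 |
|---|---|---|
| Active cell empty | 12.8 (SE 13.8) | 10.9 (SE 13.4) |
| Placebo cell empty: 6/12 v 4/12, 5/10 v 3/10, 1/2 v 1/4, 1/2 v empty | 2.333/12.333 = 18.9 (SE 13.7) | 2.533/12.733 = 19.9 (SE 13.4) |
| Stratum empty in both arms: 6/13 v 4/12, 5/11 v 3/11, 1/2 v 1/3 | 2.000/12.940 = 15.5 (SE 13.3) | 2.000/13.190 = 15.2 (SE 13.1) |

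In the last row the rule adds weight 0.5·0.5/1 = 0.25 for a stratum with nobody in it.

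**Step 4: how often, and how much.** Simulation assumptions: 39 per cohort, 2:1 allocation in blocks of 3 within strata, half the subjects with >3 UUI episodes per day, prior use capped at 19 of 39, and placebo pooled. A trigger is a stratum empty in exactly one compared arm. For 24 mg v pooled placebo:

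| Cohort 1a subjects | Prior use | Trigger |
|---|---|---|
| 0 | 30% | about 1% |
| 20 | 50% | about 3% |
| 0 | 20% | about 9% |
| 20 | 20% | about 44% (48 mg: 14%) |

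Over 0 to 30 Cohort 1a subjects and 10% to 50% prior use, the range is about 0% to 82%.

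In the triggered trials of the 44% scenario (no true difference, 40% response, 0 of 0.5):

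- The mean absolute shift is 1.4 points (0.8 at 20% response, 1.7 at 50%) and the 95th percentile is 3.3, against an SE of 13.1.
- Averaged over all trials the shift is 0.44 × 1.4 = 0.6 points.
- The mean signed shift is −1.3 when the active cell is empty and +1.1 when the placebo cell is empty. Single trials go the other way in about 20–25%.
- The SE falls by 3.2% on average, and |z| crosses 1.96 in about 1%.

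**Step 5: Protocol 9.5.1.** The trigger rates assume that its more-than-5 condition does not govern the CMH analysis. If it does, and stratum size is counted over the two compared arms, no simulated trigger is left in the 44% scenario. Counted over all three arms, about 12% of trials still trigger.

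**The case against.** The strongest reply is that the SAP states the purpose of the rule: to avoid dividing by zero. The weight never divides by zero when one arm is empty, so a reading faithful to that purpose keeps the 0.5 out of the weight, and the result is unchanged. This stands as a possible reading, but the text replaces the count itself and does not limit where the new value goes. The cited paper may settle the point; it cannot be checked here, and nothing above relies on what it says. Nor should a reader infer that the SAP misattributes the rule.

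Protocol 9.5.1 may also prevent most triggers. Its reach to the CMH analysis is arguable, so the trigger rates are conditional on it. The blinded dry-runs (SAP 2.2) and program validation (SAP 4.2.2) check programs against the plan, but they do not supply the missing instruction.

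Two stronger readings are tempting. The first is that the empty cell might be coded as 0.5 responders of 0.5, giving 14.0 instead of 10.9 in the first illustration, so that two programmers could differ by about 3 points. The SAP does not support this: it replaces the count of subjects and never puts 0.5 into the responder count. The second is that the rule favours the drug. It does not do so systematically, because the average direction depends on which arm is empty.

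**Conclusion.** The point holds in a limited form. The Mantel-Haenszel risk difference needs no 0.5. Used literally, the replacement weights a stratum that holds no comparison, shifts the estimate by about 1 to 2 points when triggered, and trims the SE by about 3%. The SE figure rests on an assumed variance formula. The trigger rates rest on assumed Cohort 1a size, prior-use share, UUI split and block size, and on Protocol 9.5.1 not applying. None of these is settled by the documents, so empty cells are possible rather than expected.

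The shift is about a tenth of the SE. The endpoints are descriptive, the p-values are nominal, and no decision rule depends on them. The documents do not support a claim that the study's conclusions are at risk. This is an optional change of the lowest priority.

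**What to change.** In SAP 6.2, delete the 0.5 replacement. State instead that any stratum with no subjects in one or both of the compared arms contributes zero to the numerator, the denominator and the variance of the common risk difference. Add a table footnote giving the number of subjects left out of each stratified estimate for this reason.

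The cost is about two sentences and one footnote. The downside is that subjects in one-arm strata do not contribute to the stratified estimate: about 2 on average, and at most 7, in the triggered trials simulated. They hold no within-stratum comparison.

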6.3. Urodynamic Endpoints

For urodynamic assessments only the independent central reviewer's interpretation will be summarized. The frequency and percentage of central reader's assessment compared to the investigator's reading and descriptive summary of the results of each parameter will be provided for baseline and Week 12. The change from baseline at Week 12 will also be provided.

6.4. hSlo cDNA concentrations

The presence and absence of hSlo cDNA concentrations will be summarized at each protocol specified visit. If present, numeric results of the concentration will also be summarized at each visit.

